15.2 Analytical Plan

Descriptive statistics will be used to describe all the study endpoints. Mean (standard deviation) and/or median (interquartile range) will be used to summarize the continuous variables. Frequencies and percentages will be used to describe categorical variables.

The primary efficacy analysis will be based on the treated, response-evaluable . All patients who meet eligibility criteria, receive at least one dose of the study drug, and have evaluable 6-month outcomes will be included in the analysis of the primary and secondary endpoints, even if there are subsequent protocol deviations. Patients who withdraw from the study before on-treatment study effects can be assessed will be replaced

Analysis of Primary Endpoints

The 6-month PFS rate and its exact two-sided 95% confidence interval (CI) will be calculated. The primary analysis will be conducted after patients have been on treatment for 6 months. As secondary analysis, we will also evaluate the 6-month PFS as a time-to-event outcome using a non-parametric (Kaplan-Meier) or parametric Weibull model, based on the distribution of the survival function.

Analysis of Secondary Endpoints

The overall survival and progression free survival probabilities will be estimated using Kaplan-Meier method. The median survival and the corresponding 95% CI will also be provided.

**Columbia University Irving Medical Center
Herbert Irving Comprehensive Cancer Center
CUMC IRB – AAAT0174**

The estimates of the overall response rate (ORR), disease control rate (DCR), best overall response (BOR), duration of response, rate of in-field local control and out of field disease progression will be provided with the corresponding 95% CIs.

153 Size/Accrual Rate

The total sample of 18 patients is expected to be accrued over the course of two years (approximately 1 patient/month).

154 Stratification Factors

No stratification factors are applicable to this study.

155 Continuous Monitoring for Toxicity

Sequential boundaries will be used to monitor the toxicity rate throughout the trial. If an excessive number of dose-limiting toxicities are seen the DSMC will have the option of halting study accrual. The boundaries at which the study is halted are listed in Table 6. This is a Pocock-type boundary that yields at most a 5% probability of crossing the boundary when the rate of dose-limiting toxicity is equal to the acceptable rate 30%. The trial will be stopped if the number of dose limiting toxicities is equal to or exceeds b_n out of n patients with completed follow-up. This boundary is equivalent to testing the null hypothesis, after each patient, that the toxicity rate is equal to 0.3, using a one-sided level 0.023 test⁵⁴.

Table 6. Continuous monitoring of toxicity using Pocock-type boundary

Number of Patients, n	1	2	3	4	5	6	7	8	9	10	11	12	13	14	15	16	17	18
Boundary, b_n	-	-	-	4	5	5	6	6	7	7	7	8	8	9	9	10	10	10

156 Reporting and Exclusions

Evaluation of toxicity

All patients will be evaluable for toxicity from the time of their first treatment with the study drug.

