2 STUDY OBJECTIVES

21 Primary Objective

- To assess the efficacy of liver-directed SBRT when added to standard of care atezolizumab+chemotherapy as measured by the progression free survival rate at 6 months

22 Secondary Objective

- To assess the efficacy of adding liver-directed SBRT as measured by overall survival, progression-free survival, and the overall response rate
- To evaluate the feasibility and safety of adding liver-directed SBRT to standard of care atezolizumab+chemotherapy
- To describe the rate of in-field local control and out of field disease progression.

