6.5.3 Data Collection and Follow-up for Withdrawn Subjects

Every effort should be made to obtain information on patients who withdraw from the study. The primary reason for withdrawal from the study should be documented in the patient's medical records. If a patient requests to be withdrawn from the study, this request must be documented in the source documents and signed by the investigator. Patients who withdraw from the study before on-treatment study effects can be assessed will be replaced. If >3 patients (~20% of projected enrollment) require replacement, enrollment will be paused for the study team to review safety data until that point to assure safe continuation of the study. If it is determined that DLTs of special interest from liver-directed SBRT are occurring at a higher rate than would be expected in previous studies of chemoimmunotherapy and liver-directed SBRT, respectively, we will implement a dose reduction of SBRT as described in Section 9.6 for an additional 3 patients and reassess the rate of toxicity before completing enrollment.

If a patient withdraws from the study, the study staff may use a public information source (e.g., county records) to obtain information about survival status.

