13.2 Definitions

Evaluable for toxicity: All patients will be evaluable for toxicity from the time of their first treatment with atezolizumab, carboplatin and etoposide.

Evaluable for objective response: Only those patients who have measurable disease present at baseline, have received at least one cycle of therapy, and have had their disease re-evaluated will be considered evaluable for response. These patients will have their response classified according to the definitions stated below. (Note: Patients who exhibit objective disease progression prior to the end of cycle 1 will also be considered evaluable.)

Evaluable Non-Target Disease Response: Patients who have lesions present at baseline that are evaluable but do not meet the definitions of measurable disease, have received at least one cycle of therapy, and have had their disease re-evaluated will be considered evaluable for non-target disease. The response assessment is based on the presence, absence, or unequivocal progression of the lesions. SBRT-treated liver lesions should not be counted as target lesions for disease response.

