13.7 Progression-Free Survival

PFS is defined as the duration of time from start of treatment to time of progression as defined by RECIST v1.1 or death, whichever occurs first. The 6-month PFS (PFS6) is defined as the proportion of patients that are progression free and alive at 6 months from the start of treatment.

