15 STATISTICAL CONSIDERATIONS

15.1 Study Design

This is a single-arm, open-label phase II study to assess the efficacy of liver-directed SBRT added to first-line atezolizumab, carboplatin, and etoposide in ES-SCLC patients as measured by 6-month PFS (primary endpoint). We hypothesize that the addition of SBRT will increase the 6-month PFS from 20% (historical control rate) to 45%. A single-stage design based on one-sided exact binomial test will be used, with a type I error of 0.10 and a power of 80%. This design requires a total of 16 evaluable patients. If at least 6 out of 16 patients have not experienced progression at 6 months, this combination therapy will be considered worthy of further study. In order to account for an estimated 10% dropout rate, 18 patients will be accrued to this study.

Primary endpoint:

- 6-month PFS rate will be defined as the proportion of patients that are progression free and alive at 6 months from the start of treatment.

Secondary endpoints:

- Overall survival (OS) will be defined as the time from treatment start to date of death or last follow up. Patients lost to follow-up at the cut-off date will be censored in the analysis.

- Overall response rate (ORR) will be defined as the proportion of patients who have a partial (PR) or complete response (CR) after beginning study treatment. Only patients who have received at least one cycle of therapy and have had their disease re-evaluated will be considered evaluable for response (see [Section 13.5.2](#)).
- Disease control rate (DCR) will be defined as the proportion of patients who have a partial (PR) or complete response (CR) or stable disease (SD) after beginning study treatment. Only patients who have received at least one cycle of therapy and have had their disease re-evaluated will be considered evaluable for response (see [Section 13.5.3](#)).
- Best overall response (BOR) will be defined as the best response recorded from the start of the treatment until disease progression (see [Section 13.5.4](#)).
- Duration of response will be defined as measured from the time measurement criteria are met for CR or PR until the first date that recurrent or progressive disease is objectively documented (see [Section 13.6](#))
- The safety and tolerability of liver-directed SBRT will be determined by reported AEs, physical examinations and laboratory tests. Frequencies of toxicities by grade according to NCI CTCAE (version 5.0) will be tabulated.

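### Section 15.2 applies an undefined 6-month evaluability condition to OS and Kaplan-Meier PFS, which conflicts with the OS censoring rule in 15.1 and leaves the direction of any bias open

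*Combined protocol and SAP*

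**What the plan says.** Section 15.2 opens its population paragraph with "The primary efficacy analysis will be based on the treated, response-evaluable" (the noun is missing in the text). It then says that all patients who meet eligibility criteria, receive at least one dose and "have evaluable 6-month outcomes will be included in the analysis of the primary and secondary endpoints". It does not define an evaluable 6-month outcome. Later in 15.2, "The overall survival and progression free survival probabilities will be estimated using Kaplan-Meier method", with no population named.

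OS and PFS are both secondary objectives in Section 2.2: "To assess the efficacy of adding liver-directed SBRT as measured by overall survival, progression-free survival, and the overall response rate".

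The OS definition in 15.1 carries its own rule: "Patients lost to follow-up at the cut-off date will be censored in the analysis". That sentence stands under OS only. PFS over time is not listed among the 15.1 endpoints. Section 13.7 takes the earlier of the two events ("PFS is defined as the duration of time from start of treatment to time of progression as defined by RECIST v1.1 or death, whichever occurs") and gives no censoring rule.

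Two other places bear on the meaning of evaluable. Section 13.2 says that patients with measurable disease who "have received at least one cycle of therapy, and have had their disease re-evaluated will be considered evaluable for response". Section 6.5.3 says that after withdrawal "the study staff may use a public information source (e.g., county records) to obtain information about survival status", and the notes to the Section 12 calendar allow the same.

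**The concern.** A condition that suits a binary 6-month endpoint is carried over to endpoints that do not need it. Kaplan-Meier estimation exists to use patients with incomplete follow-up; a population that requires a 6-month outcome removes them first. Two analysts could draw different OS curves from the same data, one following 15.1 and the other 15.2.

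Whether a patient enters the OS curve may also depend on survival itself, and survival data that the protocol collects on withdrawn patients may go unused. OS is the first-named secondary efficacy measure, and the Background quotes a 9.3-month median for this population that readers will set beside the result.

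**Working it through.** **Five patients under the two sections.**

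1. Lost completely at month 3, event-free. 15.1: censored for OS at month 3. 15.2: no 6-month outcome, so outside the set.
2. Stops imaging at month 3 without progression, known to have died at month 5. By 13.7 this is a PFS failure before 6 months, so inside the set.
3. Stops imaging at month 3 without progression, known alive at month 6. PFS6 cannot be determined, so outside the set if evaluable refers to PFS6, although 6-month survival is known.
4. Dies before any re-evaluation. Inside if every early death is an evaluable failure; outside if evaluable means response-evaluable as in 13.2. The 13.2 note that keeps progression before the end of cycle 1 does not mention death.
5. Lost at month 9 with a known 6-month outcome. Inside and censored; no conflict.

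**The plan's own figures.** For at least 6 of 16, with 20% against 45%, the exact type I error is 0.0817 and the power 0.8024. 16/0.9 = 17.8, so 18. These reproduce. The documents give no figure for OS precision or bias, so the sizes below are illustrations on stated assumptions.

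**Deletion against censoring.** Each Kaplan-Meier factor is 1 − (events)/(number at risk). Deleting a patient who is event-free at last contact leaves the events unchanged and can only reduce the number at risk. The curve therefore falls or stays the same relative to censoring.

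**Kaplan-Meier PFS at 6 months.** If nobody in the set is censored before month 6, the product of the factors collapses to k/n, the primary proportion.

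**OS when early deaths are kept and vital status is known.** Assume exponential OS with a 9.3-month median, and a fraction d who stop imaging before 6 months without progression, independently of survival. The protocol's dropout figure gives d = 0.10; d = 0.20 is an assumed upper value.

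- λ = ln 2/9.3 = 0.0745 per month; S(6) = exp(−6λ) = 0.639.
- Excluded share = d × S(6). Filtered S(6) = (1−d)S(6)/(1−d·S(6)).
- d = 0.10: 0.9 × 0.639/(1−0.0639) = 0.615. d = 0.20: 0.8 × 0.639/(1−0.128) = 0.587.
- The filtered median solves S(t) = 0.5(1−d·S(6))/(1−d): 8.77 and 8.14 months, against 9.3.

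A separate simulation of 400,000 patients used medians of 4.3 months for PFS and 9.3 for OS, exponential hazards, and an assumed 15% of PFS events being deaths. With 9% non-evaluable, 6-month OS went from 68.7% to 65.6% and the median from 9.3 to 8.8 months.

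**OS when vital status is also lost.** With dropout uniform over 0 to 6 months, the mean of S over that interval is (1−0.639)/(6 × 0.0745) = 0.806. Filtered S(6) = 0.9 × 0.639/(1−0.10 × 0.806) = 0.626, a fall of 1.3 points.

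**PFS.** Take a true 6-month value of 45%, exponential, with the same uniform loss. Here 6λ = −ln 0.45 = 0.799, and the mean of S is 0.55/0.799 = 0.689. The filtered value is 0.9 × 0.45/(1−0.0689) = 0.435 at 10% loss, and 0.8 × 0.45/(1−0.138) = 0.418 at 20%. Censoring gives 45%.

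**When early deaths are also excluded.** By hand, take 18 patients with 6 deaths by month 6: 12/18 = 66.7%. Delete 2 known survivors: 10/16 = 62.5%. Delete 1 early death as well: 10/15 = 66.7%, which cancels. Delete 2 early deaths as well: 10/14 = 71.4%, which is upward.

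In the simulation, about 9% of patients are excluded survivors and the truth is 68.7%:

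- First scan at about week 9 (Cycle 4 Day 1, as in 13.1): 8.2% early deaths, 6-month OS 72.2%, median 9.7 months.
- First scan at week 6 (closer to 5.2): 4.9% early deaths, 6-month OS 69.4%, median 9.3 months.

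**Scale.** At n = 18 the binomial standard error of 6-month OS is √(0.639 × 0.361/18) = 0.113. For the median, the approximate standard error is 1/(λ√18) = 1/(0.0745 × 4.24) = 3.2 months. At d = 0.10 the expected number excluded is 0.10 × 0.639 × 18 = 1.2 patients.

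**The case against.** The population sentence says that all such patients will be included. It does not say that only they will be, although 15.1 does use that word for ORR and DCR. A statistician could follow the more specific OS rule in 15.1 and never delete anyone. That is a sensible way out, but 15.2 names no other population for OS or PFS, so exclusion is the natural inference and should not be left to choice.

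A reader might infer that OS will be biased low. The documents do not support that as a general statement. It requires early deaths to count as evaluable and known survivors not to. Under the 13.2 sense of evaluable the bias can vanish or reverse; if evaluable means known vital status, known survivors stay in.

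A reader might also infer that 15.2 contradicts 15.1 for PFS. It does not: the 15.1 sentence covers OS only, so for PFS a rule is missing. Nor does the time-to-event analysis of PFS6 lose all independent value: 15.2 also allows a Weibull model, whose estimate need not equal k/n.

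On size, Section 5.2 requires scans to continue after treatment stops for reasons other than progression, and 6.5.3 only permits a records search. The patient who is unscanned yet known to be alive is therefore a restricted case, and giving that case the whole 10% is generous. The Synopsis calls everything beyond the primary analysis exploratory, and no OS test is planned. These points stand and limit the weight of the issue; they do not remove the conflict.

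**Conclusion.** The point holds as an inconsistency with a modest numerical effect. As written, 15.2 puts OS and Kaplan-Meier PFS behind an undefined 6-month condition, conflicts with 15.1 for OS in patients lost before month 6, and can remove patients whose survival is known. For PFS it discards event-free follow-up where no censoring rule exists.

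Relative to censoring, deleting event-free losses can only lower the curve or leave it unchanged. Relative to true OS the sign is not fixed: about 2 to 3 points low at 6 months with roughly 10% loss, if early deaths are kept, dropout is unrelated to prognosis and vital status is known; nil or upward if deaths before the first re-evaluation are also dropped. These sizes rest on assumed exponential survival and assumed loss patterns. The shift is well inside sampling error and does not change the arithmetic of the 6-of-16 rule. It is nevertheless systematic and avoidable, and its direction should not depend on a definition made after the data are seen.

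Censoring does not cure everything. If patients drop out shortly before deaths that are never captured (5% in the simulation), deletion gives 71.4% and censoring 71.7%, both above the true 68.7%.

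**What to change.** In 15.2:

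- Limit the 6-month evaluability condition to the binary PFS6 analysis, and define it. State that death or progression before 6 months is an evaluable failure.
- State that OS, PFS and the time-to-event version of PFS6 use all eligible patients who received at least one dose.
- Censor OS at the last date known alive, and PFS at the last adequate tumor assessment.
- Supply the missing noun after response-evaluable, and say whether the 13.2 definition applies.

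The cost is a few sentences. No new patients, visits or data are needed, because the protocol already provides for survival follow-up of withdrawn patients.

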16 PROTECTION OF HUMAN SUBJECTS [MULTI CENTER STUDIES]

This study is to be conducted in accordance with applicable government regulations and Institutional research policies and procedures.

This protocol and any amendments will be submitted to a properly constituted Institutional Review Board (IRB), in agreement with local legal prescriptions, for formal approval of the study conduct. The decision of the IRB concerning the conduct of the study will be made in writing to the investigator and a copy of this decision will be obtained before commencement of this study.

All subjects for this study will be provided a consent form describing this study and providing sufficient information for subjects to make an informed decision about their participation in this

**Columbia University Irving Medical Center
Herbert Irving Comprehensive Cancer Center
CUMC IRB – AAAT0174**

study. This consent form will be submitted with the protocol for review and approval by the IRB for the study. The formal consent of a subject, using the IRB-approved consent form, must be obtained before that subject is submitted to any study procedure. This consent form must be signed by the subject or legally acceptable surrogate, as outlined in the IRB approved protocol, and the investigator-designated research professional obtaining the consent.

17 STUDY FINANCES

17.1 Conflict of Interest

Any investigator who has a conflict of interest with this study (patent ownership, royalties, or financial gain greater than the minimum allowable by their institution, etc.) must have the conflict reviewed by the Columbia University Conflict of Interest Committee with a Committee-sanctioned conflict management plan that has been reviewed and approved prior to participation in this study. All CUIMC investigators will follow the University conflict of interest policy.

18 GUIDELINES FOR AFFILIATE INSTITUTIONS IN MULTICENTER STUDIES

18.1 Multi-Site Communication

The CPDM Office at CUIMC provides administration, data management, and organizational support for the affiliate sites in the conduct of a multicenter clinical trial. The CPDM Office will coordinate, at minimum, regularly scheduled conference calls with affiliate sites.

The following issues will be discussed, as appropriate:

- Enrollment information
- Cohort updates (e.g., DLTs)
- Adverse events (e.g., new adverse events and updates on unresolved adverse events and new safety information)
- Protocol violations
- Other issues affecting the conduct of the study

18.2 New Protocol Distribution, IRB Submission, Modifications, and Annual Renewals

- Protocol specific documents are distributed to affiliate sites once CUIMC IRB approval has been obtained.
- The affiliate site must submit a draft of site specific revisions to protocol and/or consent form documents for review and approval by the sponsor-investigator prior to submission to the local IRB. Draft documents should be sent to the study specific email address. The site will be provided confirmation that they are approved to submit to their local IRB.
- Protocol amendments must be approved by the affiliate site's local IRB within 90 days of distribution to the site by the sponsor-investigator.

18.3 Regulatory Documents

Prior to Site Initiation:

Sponsor-Investigator will ensure that proper requests are made of sites and that the following documentation is collected, prior to the initiation of an affiliate site.

- CV of PI, Co-I's and other research staff listed on FDA 1572 (signed and dated copy within 2 years)
- Medical Licenses of PI and Co-I's (current copy)
- Human subjects training certificates for PI and Co-I's
- CLIA/Laboratory Certifications for Local Laboratories listed on FDA 1572
- Local Laboratory Director's CV and License
- Local Laboratory Reference Ranges
- IRB roster or statement of compliance
- FDA Form 1572, if applicable (wet ink originals required)
- Financial Disclosure forms for all members listed on FDA 1572 (wet ink originals required)

Ongoing Regulatory Documentation: Sponsor-Investigator will ensure that proper requests are made of sites and that the following documentation is collected throughout the course of the study.

- IRB approval letters for all protocol modifications and all renewals
- IRB-approved consent forms
- Current IRB roster, if statement of compliance is not provided as part of site initiation
- FDA Form 1572, if applicable as updates are required
- Updated investigator and site information where relevant (e.g., CV, medical licensure and Financial Disclosure for new sub-investigator, local laboratory information)

Regulatory documents may be sent to [contact] or to the following address if wet ink originals are required:

Clinical Protocol & Data Management Office
[name]
Herbert Irving Pavilion
[name]
[name]

18.4 Site Activation

Columbia University will schedule a site initiation visit once IRB approval has been submitted from the affiliate site, if applicable.

18.5 Central Registration Procedures- Affiliate Institution Research Participant Registration Process:

All Affiliate Institutions **must** register subjects with the coordinating center (CUIMC) **prior** to any administration of study drug/intervention/local institution registration. Please see instructions below:

1. Within 48 hours of obtaining consent (excluding holidays and weekends), the Affiliate Institution CRN and/or CRC is required to submit the following documents to the CPDM Multicenter Trials Core at [contact]. The coordinating center's designee will review the documents for accurateness, and subsequently submit the documents to the CPDM Central Registration Office via email with a request to register the patient "pending eligibility." The title of the email should read, "AAAT0174 Pending Subject Registration Request (PHI)". The following documents should be submitted with the pending registration request, as applicable:
 - a. Redacted Completed/signed IRB approved/stamped Informed Consent Forms, including additional study ICFs (e.g., tissue, DNA, etc.), as applicable
 - b. Redacted Signed HIPAA (or institutional equivalent)
 - c. MCT CPDM Velos Note to File form
2. The Affiliate Institution's investigator/research nurse/data manager/coordinator must contact the coordinating center's designee (CUIMC's study specific Clinical Research Coordinator or Clinical Research Nurse) via telephone or email to communicate the following:
 - Notify of pending registration request
 - Confirm method of registration request submission (email or fax)
 - Communicate expected timeline of registration request submission (e.g., same day, next day, within the hour, etc.)
3. To complete registration, the Affiliate Institution's investigator/research nurse/data manager/coordinator should then submit the following documents to the CUIMC CPDM Multicenter Trials Core at the study listserv [contact]:
 - A signed Affiliate Site Eligibility Checklist (signed by the investigator)
 - Copies of redacted source documentation necessary for each item to be verified on the CUIMC specific Eligibility Checklist, including but not limited to:
 - Copy of required laboratory test and procedure reports (e.g., hematology, serum chemistry, pregnancy test when applicable, MRI reports, CT/bone scans, etc.)
 - Copy of pathology and surgical reports
 - Copy of clinic note(s) capturing the consent process information, along with providing source documentation of any other items needed for screening/eligibility that are not captured in other source document forms. (e.g., positive investigator statements of unique eligibility items not captured via other direct source documentation, concomitant medication lists, etc.)

**Columbia University Irving Medical Center
Herbert Irving Comprehensive Cancer Center
CUMC IRB – AAAT0174**

- Protocol deviation/waiver approvals (if applicable)
- **Please note:** subject line of email or fax should include the following: “AAAT0174 Complete Subject Registration Request (PHI)”.

4. Upon receipt of the abovementioned documents, the designated study specific Clinical Research Coordinator will review all documents and verify patient eligibility. If any questions arise during the review process, queries in the form of emails will be addressed to the applicable affiliate site study team personnel for clarification prior to enrollment. Upon verification, the CUIMC study specific designee will then forward all documents to the CPDM Central Registration Office for central registration (as described above). The CPDM Central Registration Registrar will review all applicable documents and communicate to the CUIMC study specific designee in order to clarify any items. The CUIMC study specific designee will communicate with the applicable site study team personnel for additional clarifications necessary prior to enrollment.
5. Upon receipt of the subject registration notification email, the CUIMC study specific designee will forward the notification email (which will include the study specific patient ID) to the affiliate site’s Principal Investigator, Consenting Professional, and applicable research personnel. This notification should be filed in the patient research binder accordingly. Protocol therapy **may not** be initiated prior to receipt of this notification from the coordinating center.
6. All screenfail/ineligible subjects, as well as subjects who withdraw consent prior to enrollment/initiation of protocol therapy must be submitted to the Central Registration Office in a manner analogous to the procedures noted above. Applicable source documentation will be required within the corresponding submissions.

18.6 Protocol Deviation/Subject Waiver request for Affiliate Sites:

The Affiliate site MUST submit a prospective deviation request to the CUIMC lead PI for review and submission to the HICCC DSMC and CUIMC IRB. Approvals must be obtained from all entities prior to implementation at the Affiliate site. If a prospective protocol deviation request is submitted for review (from an Affiliate site), the PI/site memo(s), HICCC DSMC approval(s) and correspondence and CUIMC IRB eligibility deviation approval letter(s) should be forwarded to the Affiliate site for documentation. The Affiliate site is also required to obtain prospective local IRB approval as per institutional policies/procedures prior to implementing the proposed deviation and registering/enrolling the subject via CUIMC Central Registration. All documents and determinations must be clearly documented in the study subject’s medical record, research chart and regulatory binder, as described. Please note that the HICCC DSMC will no longer be approving deviations to eligibility criteria.

